7.7 Exploratory PD Biomarker Endpoints and Estimands

All biomarker endpoints will be analyzed with the Integrated Analysis for the FAS using the main estimand. The main estimand will be used for all biomarker analyses, unless otherwise specified.

7.7.1 List of Biomarkers

Biomarkers are listed in [Table 7-39](#).

Table 7-39. Biomarkers List

| Biomarker Type | Biomarker |
|----------------|---|
| CSF | 
 • sTREM2 (target engagement) • IL1RA (TREM2 engagement) • Osteopontin (TREM2 engagement) • pTau217 (amyloid and Tau) • MTBR Tau-243 (amyloid and Tau) • pTau181 (amyloid)* • Aβ42 (amyloid) • Aβ40 (amyloid) • Aβ42/40 (amyloid) • GFAP (neuroinflammation and neurodegeneration) • CSF1R (microglial survival and proliferation) • NfL (neurodegeneration) • YKL-40 (neuroinflammation) • Total Tau (neurodegeneration) • IL-6 (neuroinflammation) • s100b (neuroinflammation) • Neurogranin (synapse loss) • NPTX2 (synapse degeneration) • SNAP25 (synapse degeneration) |
| Plasma | 
 • IL1RA (TREM2 engagement) • pTau217 (amyloid and Tau) • MTBR Tau-243 (amyloid and Tau)* • pTau181 (amyloid)* • Aβ42 • Aβ40 • Aβ42/40 • GFAP (neuroinflammation and neurodegeneration) • NfL (neurodegeneration) |

| Biomarker Type | Biomarker |
|---|--|
| Amyloid PET (normalized to whole cerebellum) | 
 • Composite ROIs: 
 ○ Global cortical average, SUVR measure ○ Global, centiloids measure • Roll-up ROIs, SUVR measure: 
 ○ Frontal ○ Lateral temporal ○ Lateral parietal ○ Cingulate ○ Lateral occipital |
| Tau PET (normalized to cortical grey matter of cerebellum) | 
 • Roll-up ROIs, SUVR measure: 
 ○ Medial temporal ○ Temporal ○ Frontal ○ Cingulate ○ Parietal ○ Occipital ○ Whole cortical gray cortex ○ Temporoparietal • Rowe metatemporal composite ROI, SUVR measure • Jack metatemporal composite ROI, SUVR measure |
| MRI | 
 • Volumetric parameters: 
 ○ Whole Brain ○ Hippocampus ○ Ventricles ○ Temporal cortex ○ Parietal cortex |

CSF = cerebrospinal fluid; MRI = magnetic resonance imaging; PET = positron emission tomography; ROI = region of interest; SUVR = standardized uptake value ratio.

*if available

7.7.2 Descriptive Summaries of Biomarker Endpoints

The integrated descriptive summary of a biomarker endpoint including the Placebo Data will summarize all the data collected in the Core Study and in the LTE Study with descriptive statistics, by individual placebo/TC, AL002 15 mg/kg, 40 mg/kg, and 60 mg/kg, and the TC treatment groups, and AL002 40 and 60 mg/kg combined group.

The CFB and PCFB will be based on the Core baseline for placebo/TC, AL002 15 mg/kg, 40 mg/kg, and 60 mg/kg, and AL002 40 and 60 mg/kg combined treatment groups. The CFB and PCFB for the TC will be based on the LTE baseline. And all analysis visits from the Core and LTE Studies will be included.

The integrated descriptive summaries for Tau PET parameters will be based on the subset with redefined core baseline (participants with either pre-dose Tau PET in the Core study if available or the first evaluable post-dose Tau PET scan result in the Core study if pre-dose PET scan in the Core study is missing).

Longitudinal trend (line-plot) figures (group mean [unadjusted] of change from Core baseline \pm SEM over time at each analysis visit) over the Core + LTE periods for placebo/TC, AL002 15 mg/kg, 40 mg/kg, and 60 mg/kg treatment groups will be created.

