**Description of Study Periods and Visits:**

*Screening/Baseline Period: Prior to AL002-LTE Study Entry (from Day -28 to Day -1)*

As described in the sections above, the participant and/or their study partner may sign the informed consent/assent for AL002-LTE during the final dosing visit of the parent study. This will mark the beginning of the screening/baseline period for AL002-LTE. Required safety and/or eligibility assessments may be obtained at any time prior to dosing on Day 1/Week 1. The screening/baseline period may also be utilized to obtain any efficacy assessments (eg, COAs) that were not collected from the parent study in the last 12 weeks prior to Day1/Week 1. For those participating in the amyloid or Tau PET sub-studies in the AL002-2 trial, a new longitudinal amyloid and Tau PET imaging will be required if the last timepoint from the parent study was taken more than 24 weeks prior to Day 1/Week 1. Baseline MRIs are required if the last MRI occurred more than 90 days prior to the first dose on Day 1/Week 1 of AL002-LTE. For those participating in optional CSF sampling, an optional LP will need to be collected prior to Day 1/Week 1 if it has been more than 12 weeks since the last evaluation. The C-SSRS must be completed during the screening/baseline period.

Once eligibility is confirmed and the appropriate safety assessments have been collected, enrollment can occur any time after signing the informed consent and prior to the AL002-LTE first dose on Day 1/Week 1.

Participants will be offered the opportunity to consent for the optional exploratory biomarker assessments (CSF sampling, longitudinal Amyloid PET and Tau PET) even if they did not previously agree in the parent study. Details for the optional PET imaging assessments including objectives, eligibility criteria, sample collection, and imaging specifications are provided in the PET Imaging Procedures Manual. Consent for the optional assessments will be documented. Participation in the optional PET imaging procedures will be allowed according to local country regulations. The screening/baseline period can be utilized to capture the initial timepoint, which will serve as the participant's baseline and will not be used to determine eligibility.

*Treatment Period (Day 1/Week 1 to Week 49)*

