- cc. If an LP and an MRI are performed in the same visit, either (a) the MRI should be performed first or (b) the MRI should be performed at least 3 days after the LP. This minimizes the effect of CSF removal on brain volume measurements. If an LP and a PET scan are performed in the same visit, either (a) the LP

should be performed first or (b) the LP should be performed at least 12 hours after the PET scan. Participants who undergo both Tau PET and Amyloid PET exams at a given study visit must receive these exams on different calendar days.

dd. New longitudinal Amyloid and Tau PET imaging are required as the baseline scan for longitudinal Amyloid and Tau PET imaging if the participant opts in to the optional procedures unless already obtained within 24 weeks before Day 1/Week 1 in study AL002-2. PET imaging has a window of  $\pm 28$  days (longer than the standard visit window). Tau PET scans or Amyloid PET scans should not be performed if local restrictions for radiation exposure would be exceeded; if applicable, the site should contact the Sponsor to discuss alternative timing of Tau PET or Amyloid PET scans.

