| Analysis Visit | Target Day | T-T Analysis Visit Window | P-TC Analysis Visit Window ^b |
|----------------|------------|---------------------------|---|
| Core Baseline | 1 | ≤ 1 | ≤ 1 |
| Week 48 | 337 | [2, 421] | [2, min (421, LTE Day 1)] |
| Week 72 | 505 | [422, 589] | [422, min (589, LTE Day 1)] |
| Week 96 | 673 | [590, 771] | [590, LTE Day 1] |
| Week 124 | 869 | [772, 981] | LTE Week 24 |
| Week 156 | 1093 | > 981 | LTE Week 56 |

^a Target Day and Core Study Day are based on Core Study Day 1.

^b LTE Day 1 represents Core Study Day of first dose date of LTE Study. If no such date, use Core study day of the last visit date among Core visits and LTE screening visit. LTE Weeks are from [Table 7-35](#).

Table 7-35. Analysis Visit Windows for Tau PET Assessments Based on LTE Study Day ^a

| Analysis Visit | Target Day | Analysis Visit Window |
|----------------|------------|-----------------------|
| LTE Baseline | 1 | ≤ 1 |
| LTE Week 24 | 169 | [2, 281] |
| LTE Week 56 | 393 | > 281 |

^a Target Day and LTE Study Day are based on LTE Study Day 1.

Table 7-36. Analysis Visit Windows for Tau PET Assessments, Redefined Baseline ^a (Sensitivity Analysis)^b

| Analysis Visit | Target Day | T-T Analysis Visit Window | P-TC Analysis Visit Window ^c |
|----------------|------------|---|---|
| Baseline_R | 1 | ≤ Day 1 Predose, if it exists. If not, then first day of non-missing result (up to Day 421) | |
| Week_R 48 | 337 | [2, 421] | [2, min (421, LTE Day 1)] |
| Week_R 72 | 505 | [422, 589] | [422, min (589, LTE Day 1)] |
| Week_R 96 | 673 | [590, 771] | [590, LTE Day 1] |

| | | | |
|------------|------|------------|-------------|
| Week_R 124 | 869 | [772, 981] | LTE Week 24 |
| Week_R 156 | 1093 | > 981 | LTE Week 56 |

^a Target Day and Core Study Day are based on Core Study Day 1.

^b Redefined baseline: baseline corresponds to either the pre-dose visit (prior to dosing) in Core Study if the pre-dose Tau PET scan is evaluable, or 1st postdose scan in Core Study if the pre-dose Tau PET scan is missing.

^c LTE Day 1 represents Core Study Day of first dose date of LTE Study. If no such date, use Core study day of the last visit date among Core visits and LTE screening visit. LTE Weeks are from [Table 7-35](#).

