7.1.2 Selection of Data for LTE Baseline

The LTE baseline value will be chosen based on the rules specified below, unless otherwise specified. Note that LTE Baseline is applicable only to Group P-TC, unless otherwise specified.

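### The Tau PET descriptive summaries require a Core Study scan even in the Titration Cohort column, which measures change from LTE baseline, so former placebo participants who first opt in at the LTE are left out of it

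*SAP*

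**What the plan says.** SAP 7.7.2 sets out the integrated biomarker summaries. The placebo/TC, 15, 40, 60 and combined 40 and 60 mg/kg columns use Core baseline. A separate Titration Cohort column does not: "The CFB and PCFB for the TC will be based on the LTE baseline". SAP 7.1.2 agrees on who has such a baseline: "Note that LTE Baseline is applicable only to Group P-TC, unless otherwise specified".

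The next paragraph of 7.7.2 then sets the population for Tau PET: "The integrated descriptive summaries for Tau PET parameters will be based on the subset with redefined core baseline". It defines the subset as "participants with either pre-dose Tau PET in the Core study if available or the first evaluable post-dose Tau PET scan result in the Core study", the second option applying when the pre-dose scan is missing. No column is excepted. The section places no comparable restriction on amyloid PET or CSF.

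SAP Table 7-35 defines Tau PET windows by LTE study day: LTE baseline, LTE Week 24 and LTE Week 56. Table 7-36, which is titled a sensitivity analysis, defines the redefined baseline by Core study day.

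On the protocol side, the synopsis (Screening/Baseline Period) says: "Participants will be offered the opportunity to consent for the optional exploratory biomarker assessments". This applies even to those who declined in the parent study. Table 9 footnote dd adds: "New longitudinal Amyloid and Tau PET imaging are required as the baseline scan for longitudinal Amyloid and Tau PET imaging", unless a parent-study scan was obtained in the 24 weeks before LTE Day 1. Footnote bb plans at least one repeat scan after a baseline Tau PET.

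**The concern.** A Core Study scan plays no part in a change from LTE baseline. For the columns based on Core baseline, the redefined baseline is helpful, because it keeps participants who lack a pre-dose scan. For the Titration Cohort column it can only remove people whose change is computable.

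Those at risk are the former placebo participants who accept the LTE invitation to join the Tau PET assessment for the first time. If they are left out, the column describes fewer participants than were scanned, selected by whether they had a Core scan and not by whether they have the data the column needs.

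**Working it through.** The plan states no figure to reproduce. The check applies its rules to one type of participant, then gives an illustrative precision range.

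**1. Rule check.** Take a former placebo participant with no Core Tau PET scan, an LTE screening scan, and a scan at LTE Week 24 or Week 56.

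| Rule | Source | Result |
|---|---|---|
| May opt in first at the LTE | Protocol synopsis, Screening/Baseline Period; Section 3.1 | Yes |
| New baseline scan required | Protocol Table 9, footnote dd | Yes |
| At least one repeat scan planned | Protocol Table 9, footnote bb | Yes |
| LTE baseline applies to this group | SAP 7.1.2 | Yes |
| LTE Tau PET windows exist | SAP Table 7-35 | Yes |
| Baseline and post-baseline value available for change | SAP Section 5, opening paragraph | Yes |
| Has a Core Study scan, so is in the subset | SAP 7.7.2 | **No** |

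The participant meets every condition for change from LTE baseline and fails only the Core-scan condition.

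**2. Could the LTE screening scan count as the redefined Core baseline?** Study day = 7 × week + 1, so Week 60 is Day 421, Week 96 is Day 673 and Week 100 is Day 701. After a full 96-week Core treatment period, an LTE screening scan falls at about Core Day 673 to 701, past the limit in the Table 7-36 cell. With a much earlier LTE entry the cell alone might admit it. However, footnote b of that table restricts the fallback to the "1st postdose scan in Core Study if the pre-dose Tau PET scan is missing", and 7.7.2 also requires a Core scan.

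**3. Is the change picked up elsewhere in SAP 7.7?**
- The Tau PET MMRM and pMMRM (7.7.3) use the same subset, stop at Week 96, and take only Core and LTE screening data for placebo.
- The supportive-estimand Tau PET analyses (7.7.3) use the same redefined-baseline subset.
- The trend figures and the placebo/TC column (7.7.2) use change from Core baseline, which cannot be computed without a Core scan.
- Section 7.7 specifies the Integrated Analysis only. Table 2-1 mentions LTE analyses of biomarkers, but 7.7 defines none for Tau PET.

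The Titration Cohort column is therefore the only place where this change could be summarised.

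**4. Precision range (assumption).** The documents give no opt-in counts. Let g be the share of Titration Cohort baseline/follow-up pairs excluded. With the same standard deviation, the standard error grows by 1/√(1 − g) − 1:

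| g | Increase in SE |
|---|---|
| 0 | 0% |
| 0.1 | 1/√0.9 − 1 = 5.4% |
| 0.2 | 1/√0.8 − 1 = 11.8% |
| 0.3 | 1/√0.7 − 1 = 19.5% |
| 0.4 | 1/√0.6 − 1 = 29.1% |

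**5. The Day 421 limit.** The Table 7-36 cell reads: "If not, then first day of non-missing result (up to Day 421". Footnote b and 7.7.2 give the same fallback without a day limit. A participant first scanned in the Core Study after Day 421 is outside the subset under the cell and inside it under the other two.

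**The case against.** The best defence is that the SAP redefines which scan serves as Core baseline, and so speaks only to columns that use Core baseline. The preceding paragraph separates those columns from the Titration Cohort column, and Section 5 already supplies the inclusion rule for change. This may well be what was intended. But the sentence bases the Tau PET summaries on a subset of participants and exempts no column, so a programmer following the text would apply the filter throughout.

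A second defence is that requiring a Core scan keeps the placebo/TC and Titration Cohort columns on a common pool. That is a reasonable aim, but the SAP does not state it.

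The objection that little is at stake largely stands. Tau PET is optional and exploratory. On-AL002 scans in the Titration Cohort enter no model or treatment comparison. First-time opt-ins are further limited by country rules, tracer supply and radiation limits, so there may be none.

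A reader might infer more than the documents support, in three ways:
- **That Core participants first scanned after Day 421 are also excluded.** The texts disagree on this, so it is unclear.
- **That these participants undergo scans whose data are never used.** The documents do not say so. SAP 7.5 leaves room for exploratory PK/PD work under a separate plan, and absence from one column is not absence from all use.
- **That former active participants without a Core scan are wrongly dropped too.** Their change is defined from Core baseline, so their absence follows from the definition.

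**Conclusion.** The point holds as a minor one. Read literally, SAP 7.7.2 removes first-time LTE opt-ins from the Titration Cohort Tau PET column although their change from LTE baseline can be calculated, and no other planned summary or model includes their change on AL002.

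The consequence is confined to one exploratory descriptive column. Its size is unknown and may be nil; the 5% to 29% range for the standard error rests on an assumed 10% to 40% of pairs excluded and on an unchanged standard deviation. No bias has been shown. The disagreement over Day 421 is a separate inconsistency in the SAP. It needs reconciling but does not affect the finding on first-time opt-ins, whom 7.7.2 and footnote b exclude in any case.

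**What to change.** In SAP 7.7.2, limit the redefined-core-baseline subset to the columns based on Core baseline: placebo/TC, 15, 40, 60, and combined 40 and 60 mg/kg. State that the Titration Cohort column includes every Titration Cohort participant with an evaluable LTE-baseline Tau PET scan under Table 7-35 and at least one later LTE scan.

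Separately, make the Table 7-36 cell, its footnote b and 7.7.2 agree on whether the Day 421 limit applies.

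The cost is one sentence, a different subset flag for one column, and a small edit to reconcile Day 421. No study procedure changes. The placebo/TC and Titration Cohort columns will have different Ns, which a footnote should explain. Participants whose first Tau PET scan comes after LTE dosing has begun, which protocol Table 9 footnote bb allows with sponsor agreement, would still have no LTE baseline and would stay out of the column.

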7.7.3 Pharmacodynamic (PD) Assessment of Biomarker Endpoints

For Integrated Analysis, similar analyses listed in section 7.6.2 for efficacy endpoints will be provided for biomarker endpoints. Specifically, for CSF and plasma biomarkers, volumetric MRI, amyloid PET and Tau PET parameters [Table 7-39], the analyses will be based on the integrated data up to Week 96 since the initiation of study treatment from both the Core Study and the LTE study for the treatment groups and the data from the Core Study and the LTE screening data for the placebo treatment group. Specifically, the MMRM will be fit with CFB in biomarkers up to Week 96 as the dependent variable, and treatment group, categorical visit, visit-by-treatment interaction, baseline (from the Core Study) biomarker, and APOE e4 status of carrier vs. non-carrier as fixed effects.

Input for the models will be non-missing data at all analysis visits up to and including Week 96, as specified in Tables Table 7-12, Table 7-28, Table 7-30, Table 7-32, and Table 7-36. Treatment comparisons will be reported for specified visits as indicated below:

- Plasma biomarkers:
 - AD-pathology (A β 42/40, pTau217): week 12, 24, 48, 72 and 96
 - AD-pathology (MTBR Tau-243 [if available]): week 12, 24, 48, 72 and 96
 - AD-pathology (pTau181 [if available]): week 16, 36, 60 and 84
 - Target engagement (IL1RA): week 1, 2, 4, 6, 8, 12, 24, 36, 48, 72 and 96
 - Neurodegeneration (NfL, GfAP): week 12, 24, 48, 72 and 96
- CSF biomarkers: week 6, 48, 72 and 96
- Amyloid PET parameters: week 48 and 96
- Tau PET parameters: week 48, 72 and 96
- Volumetric MRI parameters: week 48, 72 and 96

Model results, including treatment comparisons will also be obtained as “overall” for the average over all analysis visits in the model.

For Tau PET parameters [Table 7-39], a pMMRM model will be additionally conducted. The integrated PD analyses via MMRM and pMMRM will be based on the subset with redefined core baseline.

For amyloid PET centiloids, the number of participants with amyloid clearance (positive [centiloid \geq 24.1] at core baseline and negative [centiloid < 24.1] post core baseline (separately for week 48 and week 96), and percentage with 95% CI (exact mid-p method), will be summarized based on the integrated data up to Week 96 since the initiation of study treatment from both the Core Study and the LTE study for the treatment groups and the data from the Core Study and the LTE screening data for the placebo treatment group. Treatment comparison (vs. placebo) at week 48 and week 96 will be based on the exact mid-p method.

Additional integrated analyses based on supportive estimand will be provided for Tau PET parameters (descriptive summary, MMRM and pMMRM) [Table 7-39] for the subset with redefined baseline, and amyloid PET parameters (descriptive summary and MMRM) [Table 7-39].

The MMRM and pMMRM modeling analyses will not be performed at the first IA at the time of unblinding of the Core Study due to limited data from the LTE study at this IA, but will be performed in all analyses after the first IA.

7.8 Immunogenicity Endpoints

The exploratory analyses for immunogenicity endpoints will be performed on the Non-e4/e4 Set participants who had at least one post-baseline sample evaluable for immunogenicity.

7.8.1 Antidrug Antibodies (ADAs)

Blood serum samples will be collected for determination of ADAs. In addition to titer numerical results, blood serum results will be classified as Positive, Negative or Unknown (missing, non-evaluable, etc.).

The number and percentage of participants having positive or negative results will be summarized by visit and treatment group. The titer numerical results will be descriptively summarized by visit and treatment group. Shift from baseline in blood serum classes will be summarized by visit (refer to Table 7-20 and Table 7-21 for analysis visit window definitions) and treatment group using the frequency count and percentage of participants in each category.

A listing of ADAs including all participants with available ADA data will be provided.

